4. SAMPLE SIZE CONSIDERATION

The assumption for the sample size determination was estimated using the Package Inserts of Durezol®, Lotemax® and Inveltys® and results from the APP13007 Phase 2 study (CPN-201). The sample size for ACC count primary efficacy endpoint is based on the assumption of 26% of subjects in APP13007 group with ACC Count = 0 at POD8 and maintained through POD15 and 12% of subjects in the matching vehicle placebo group. The two-group Chi-square test, with a two-sided significance level of 5% and 92% power, requires 175 subjects per treatment group to detect the difference between APP13007 and placebo.

The same sample size using the assumption of 57% of subjects with Ocular Pain Grade = 0 at POD4 and maintained through POD15 in APP13007 group and 38% of subjects in the placebo group will provide 95% power to detect the treatment difference.

With an estimated 5% dropout rate, this study will randomize approximately 185 subjects per treatment group for a total of approximately 370 subjects.

5. ANALYSIS POPULATIONS

The analysis populations are defined below.

5.1 Intent-to-Treat (ITT) Population

The ITT population will consist of all subjects who are randomized to the study drug.

Following the ITT principle, subjects will be analyzed according to the treatment assignment at randomization.

5.2 Per-protocol (PP) Population

The PP population will consist of all subjects in the ITT population who (i) receive at least 1 dose of study drug, (ii) do not have major protocol deviations that would impact the evaluation of efficacy, and (iii) have at least 80% overall treatment compliance.

The subjects who are to be excluded from the PP population will be identified prior to database lock and unmasking of the treatment assignment and the reason for exclusion will be documented and listed.

5.3 Safety Population

The safety population will consist of all randomized subjects who receive at least one dose of study drug.

Subjects will be analyzed in the safety analysis according to the treatment actually received.

6. DATA ANALYSIS CONSIDERATIONS

6.1 General Consideration

All statistical analyses and generation of tables, figures, subject data listings, and statistical output will be performed using SAS Version 9.3 or higher.

6.2 General Presentation of Summaries and Analyses

Descriptive statistics will be displayed to provide an overview of the study results. For categorical variables, the number and percentage of subjects in each category will be presented. Unless otherwise noted, all percentages will be displayed to 1 decimal place. No percentage will be displayed for zero counts, and no decimal will be presented when the percentage is 100%. For continuous variables, descriptive statistics will include number of subjects with available measurements (n), mean, standard deviation, median, first quartile (Q1), third quartile (Q3), minimum, and maximum.

Decimal places for descriptive statistics will apply the following rules unless otherwise stated:

- “n” will be an integer
- Mean, standard deviation, and median will use one additional decimal place compared to the original value
- Minimum and maximum will have the same number of decimal places as the original value

Continuous variables will be examined to ensure that they meet the required assumptions for the intended statistical analysis method. If the statistical assumptions are violated, alternative analytical methods, such as nonparametric statistics, will be used.

Unless otherwise specified, all statistical tests will be two-sided and the statistical significance will be tested at the 5% level ($\alpha = 0.05$). Statistical tests of efficacy variables will be presented as two-sided p-values rounded to three decimal places. P-values less than 0.001 will be presented as “<0.001” and p-values greater than 0.999 will be presented as “>0.999”.

6.3 Data Handling Rules

6.3.1 Baseline Values

Baseline values is defined as the values obtained at the most recent assessment prior to the first dose of the study drug. Both scheduled and unscheduled visits will be considered.

Screening values will be considered as the baseline values when the change from screening is of interest.

6.3.2 Study Eye

Each subject’s study eye is defined as the eye that undergoes cataract surgery in the study.

6.3.3 Non-Study Eye

Each subject's non-study eye is defined as the eye that does not have cataract surgery in the study.

6.3.4 Study Day and End of Study (EOS)

Study Day for each subject is calculated relative to the date of the first dose of study drug:

- Study Day = Visit Date/Event Date - Date of First Dose +1
When the Visit Date/Event Date is on or after the Date of First Dose
- Study Day = Visit Date/Event Date - Date of First Dose
When the Visit Date/Event Date is prior to the Date of First Dose

Study Day will be used to define analysis windows for efficacy analyses and to evaluate the timing of events or measurements occurring relative to the first dose of study drug.

Study Day ‘-1’ corresponds to Surgery Day 0 and Study Days ‘-29’ to ‘-2’ correspond to Screening Visit (Days -28 to -1) as shown in the Schedule of Events ([Table 2](#)).

EOS is defined as the last visit in the study. EOS will be either Visit 6/POD22 for subjects who complete the study or the Early Termination/Withdrawal visit for subjects who discontinue the study prior to Visit 6/POD22.

6.3.5 Analysis Visit for Efficacy Analyses

The use of efficacy data collected in the study will be maximized by including the assessments that are performed outside the planned visit window. Each Analysis Visit (POD 4, 8 and 15) will use an analysis window to determine the efficacy data that will be used to derive the efficacy endpoints. The actual Study Day ([Section 6.3.4](#)) will be used to define the analysis window. The analysis window for each Analysis Visit is shown in Table 3.

Table 3: Analysis Windows for Efficacy Analysis

Analysis Visit	POD4	POD8	POD15
Study Days in Analysis Window	2 – 6	7 – 11	12 – 17 or Scheduled Visit*

* Only for subjects who (i) complete at least 14 days of dosing, (ii) do not use rescue medication and (iii) have a scheduled POD15 visit after Study Day 17

If the efficacy assessments are performed at unscheduled visits occurring after Visit 2/POD1 and before Visit 5/POD15, the date of the unscheduled visits will also be used to determine the appropriate analysis window.

The efficacy assessments performed after two days following the last dose of study drug will not be used when the subjects have administered less than 14 days of study drug.

When multiple efficacy assessments fall within the same analysis window for an Analysis Visit (see [Table 3](#)), the following rules will be applied:

- If two scheduled assessments fall within the same analysis window for an Analysis Visit and one of the Analysis Visits (either before or after the Analysis Visit with two scheduled assessments) has no scheduled assessment, then the scheduled assessment data will be used for the Analysis Visit without an assessment. For example, when a subject has a scheduled POD4 visit at Study Day 3 and a scheduled POD8 visit at Study Day 6, the Analysis Visit POD4 would have two scheduled assessments and the Analysis Visit POD8 would have no data. In this case, the scheduled POD8 visit assessments will be used for the Analysis Visit POD 8.
- If one scheduled assessment and at least one unscheduled assessment fall within the same analysis window for an Analysis Visit, the latest value in the analysis window will be used for all relevant efficacy analyses.

The definition of the Analysis Visit for the efficacy analyses will be re-examined prior to database lock. If there is a need to adjust the analysis window in Table 3, the SAP will be amended to document the changes.

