9.4.2 Management

Investigators will use clinical judgment to determine when to rescue a subject using the guidance provided in [Section 9.4.1](#) and the appropriate rescue medication to use. All rescued subjects will stop study drug at the time of rescue and will continue in the study through completion of the Visit 6 (POD22) assessments ([Table 1](#)).

If a subject needs to be rescued at Visit 5 (POD15), the Visit 5 (POD15) assessments ([Table 1](#)) should be completed before the subject is administered rescue medication.

Rescued subjects will be considered treatment failures, and the need for rescue medication will not be considered as an AE.

An AE occurring at the time of rescue will be recorded in the eCRF and will be followed by the Investigator to stabilization or resolution of the AE or the end of the study (whichever comes last).

If a subject is rescued, this event will be recorded in the eCRF (not as an AE). Medications used for rescue will be recorded in the ConMeds section of the eCRF, indicating that they were used for rescue.

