6.4.2 Rescued Subjects

Any subject not responding to the study drug because of lack of efficacy at any time after randomization at Visit 2/POD1 may be rescued and placed on an appropriate alternative therapy determined by the Investigator.

The efficacy assessments performed after starting rescue medication will be excluded from the efficacy analyses.

For the primary efficacy endpoints, subjects who are rescued at any time after the first dose of study drug and before the efficacy assessments at POD15 will be considered as treatment failures (Non-responders). The same approach will be applied to derive the secondary endpoint of sustained ACF grade =0.

For both categorical and continuous secondary efficacy endpoints of ACC grade, ocular pain grade and ACF grade, the last observation carried forward (LOCF) approach will be used to impute the data for each Analysis Visit after starting rescue medication.

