6.4.3 Handling Dropouts or Missing Data

6.4.3.1 Imputation of Missing Efficacy Data

The missing data handling rule for the study eye will be applied for the efficacy endpoints.

Missing data from subjects who discontinue the study before POD15 assessments without taking rescue medication:

For subjects who prematurely discontinue the study without taking rescue medication, the LOCF approach will be used to impute the missing data. The last observation will be the last assessment value after the first dose of study drug and up to two days following the last dose of study drug.

Missing data from subjects who discontinue the study and take rescue medication before POD15 assessments:

For both categorical and continuous secondary efficacy endpoints of ACC grade, ocular pain grade and ACF grade, subjects who take rescue medication before POD15 assessments and prematurely discontinue the study, the LOCF approach will be used to impute the missing data. The last observation will be the last assessment value after the first dose of study drug and prior to starting rescue medication.

Intermittent missing data:

The likelihood of having intermittent missing data is low. For subjects with intermittent missing data for efficacy endpoints, the LOCF approach will be applied to impute the missing data, i.e., using the data collected from the most recent prior visit after the first dose of study drug.

If no data can be carried forward (i.e., missing assessments at POD 4 visit or no available post-baseline assessments), missing data will be treated as missing for the continuous endpoints and will be considered as 'Non-responder' for the categorical endpoints.

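### The rescue condition in the SAP Table 3 footnote has no time limit, so a valid late POD15 reading taken before rescue is discarded and the POD8 value stands in for it (wrong as written; minor)

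*SAP*

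**What the plan says.** - **SAP 6.3.5, Table 3 and footnote.** The POD15 analysis window is Study Days 12–17. A later scheduled visit is allowed only if the subject completed at least 14 days of dosing and meets two further conditions: "ii) do not use rescue medication and (iii) have a scheduled POD15 visit after Study Day 17".
- **SAP 6.4.2.** "The efficacy assessments performed after starting rescue medication will be excluded from the efficacy analyses". For the primary endpoints and sustained zero flare, a subject is a failure if rescued after the first dose and before the POD15 efficacy assessments. For the by-visit cell, pain and flare endpoints, rescued subjects are handled by last observation carried forward (LOCF).
- **SAP 6.4.3.1.** "For subjects with intermittent missing data for efficacy endpoints, the LOCF approach will be applied to impute the missing data", taking the value from the most recent earlier post-dose visit.
- **Protocol 9.4.2.** For a subject who needs rescue at Visit 5, the assessments of that visit "should be completed before the subject is administered rescue medication". The same section, like Protocol 5.4.1, calls rescued subjects treatment failures without a time limit. Rescued subjects stay in the study to Visit 6.
- **Protocol 10.3.2.** Failure on the primary endpoints is tied to rescue before Visit 5.
- **SAP 10.1.3, item 5.** Missing data in subjects who take rescue are not counted as missing, on the ground that these subjects are already non-responders.

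**The concern.** A subject rescued before a late Visit 5 is already dealt with by SAP 6.4.2: failure on the primary endpoints, later readings excluded. For that subject condition (ii) adds nothing. It has an effect of its own only when rescue starts at or after a late Visit 5, once the assessments are done. There it removes a reading that 6.4.2 would keep.

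What is at stake is whether an event after the assessment should decide if the assessment counts. The second half of each primary endpoint exists to detect loss of response by POD15. A reading that shows such a loss should not be replaced by an older zero. Nor should a reading that shows clearance be replaced by an older non-zero value.

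**Working it through.** **1. Which readings are late.** Study Day counts from the first dose, which is given on POD1, so Study Day and POD number agree. Visit 5 is allowed on POD15 or POD16. A reading on Study Day 18 or later is at least 2 days past the visit window.

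**2. The rules applied to one subject.** 14 days dosed; 0 cells at POD8; no reading on Days 12–17; Visit 5 on Day 18 shows cells; rescue starts after the assessments.

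| Rule | Result |
|---|---|
| Protocol 9.4.2 | The Day 18 reading precedes rescue |
| SAP 6.4.2, exclusion of readings | Not excluded |
| Table 3 footnote, condition (ii) | Barred, because the subject uses rescue |
| Analysis Visit POD15 | Empty |
| SAP 6.4.2 and 6.4.3.1, by-visit endpoints | POD8 zero carried to POD15 |
| SAP 6.4.2, primary failure rule | Rescue came after the Visit 5 assessments, so literally not met |
| SAP 6.4.3.1, primary endpoint | POD8 zero carried forward: responder, on the literal reading |

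With Visit 5 and rescue both on Day 17, the non-zero reading is in the window and the subject is a non-responder. For pain the pattern is the same, with zeros at POD4 and POD8.

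**3. The opposite case.** POD8 non-zero; late Visit 5 shows 0 cells; rescue then starts for pain. The zero is barred, the POD8 value is carried forward, and the by-visit POD15 result is a false non-response.

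**4. The plan's own figures.** Inputs from SAP 4: "assumption of 26% of subjects in APP13007 group with ACC Count = 0 at POD8 and maintained through POD15"; "12% of subjects in the matching vehicle placebo group"; "two-sided significance level of 5% and 92% power, requires 175 subjects per treatment group"; for pain, "57% of subjects with Ocular Pain Grade = 0 at POD4 and maintained through POD15 in APP13007 group and 38% of subjects", with 95% power stated.

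n = [1.960·√(2p̄q̄) + 1.405·√(p₁q₁ + p₂q₂)]² / (p₁ − p₂)², with p̄ = 0.19:

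n = [1.960·√0.3078 + 1.405·√0.2980]² / 0.14² = 175.4, or 176 rounded up (stated 175).

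Power at 175 per arm is 91.9% for cells and 94.8% for pain (stated 92% and 95%). 175/0.95 rounds up to 185 per arm. The plan's figures reproduce, and none of them depends on the footnote.

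**5. How many subjects.** The documents give no rate of late visits or of rescue at them. Assume that 1–5% of Visit 5s fall after Day 17 and that 2–10% of those subjects are rescued at or after that visit:

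- low: 370 × 0.01 × 0.02 = 0.07
- high: 370 × 0.05 × 0.10 = 1.85

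That is about 0.1 to 2 subjects over both arms. For the primary cell endpoint the number is smaller still, because the subject must also have had zero cells at POD8. One subject is 1/185 = 0.54 percentage points of an arm.

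**6. Effect on the cell test.** The planning rates give 0.26 × 185 ≈ 48 and 0.12 × 185 ≈ 22 responders. With equal arms, Pearson χ² = 370·d² / [T(370 − T)], where d is the difference and T the sum of the responder counts.

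| APP13007 vs placebo | Change | p |
|---|---|---|
| 48 vs 22 | none | 0.0006 |
| 48 vs 23 | 1 placebo | 0.0010 |
| 48 vs 24 | 2 placebo | 0.0016 |
| 50 vs 22 | 2 active | 0.0002 |
| 48 vs 32 | 10 placebo | 0.043 |
| 48 vs 33 | 11 placebo | 0.059 |

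At the planning rates, 11 placebo-only reclassifications are needed to lose significance. One subject decides the test only at a boundary: 48 vs 32 against 48 vs 33, or, on the active side, 35 vs 22 (p = 0.061) against 36 vs 22 (p = 0.045).

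**7. Effect on power.** Power at 185 per arm is 93.3%. If an assumed 1% of an arm (about 2 subjects) were reclassified as responders, it would be 88.7% for placebo only, 92.3% for both arms and 95.7% for APP13007 only.

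**The case against.** The strongest reply is that no text says the relapsing subject is a primary responder, and several places point the other way. Protocol 5.4.1 and 9.4.2 call every rescued subject a failure. SAP 10.1.3 item 5 takes it as given that rescued subjects are non-responders. SAP 6.4.2 can itself yield failure: if the Day 18 reading does not count as a POD15 assessment, rescue began with no qualifying POD15 assessment before it. Condition (ii) might also be meant as status up to the visit, in keeping with the stated aim in 6.3.5 of making the most of the efficacy data. All of this is fair. A reader might infer that the SAP settles the matter and scores observed relapses as successes. The documents do not support that; they leave conflicting rules.

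A reader might also infer that the error always favours APP13007. It does not. Step 3 of the working shows a false non-response, and false responders on placebo would dilute the effect.

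There are safeguards. The additional analysis in SAP 10.1.4 counts the relapsing subject as a failure whether the Day 18 reading is used or treated as missed. SAP 10.1.2 tabulates responders with imputed data separately. SAP 6.3.5 promises a re-examination of the analysis visits before database lock.

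The objection does not remove two things. The by-visit endpoints in the SAP have only carry-forward rules for rescued subjects, so the older value stands there whatever the primary status. And reading 6.4.2 as failure creates its own anomaly: a subject with zero cells at POD8 and at a late Visit 5, rescued later for another reason, becomes a failure despite two observed zeros. The tipping-point analysis gives no check, because item 5 treats rescued subjects as already classified.

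**Conclusion.** Wrong as written, and minor. Condition (ii) discards a valid pre-rescue observation and disagrees with the exclusion rule in SAP 6.4.2. For the by-visit cell, pain and flare endpoints the consequence follows from the SAP: the POD8 value replaces the observed one. For the primary endpoints it is an unresolved conflict, in which the literal reading of 6.4.2 and 6.4.3.1 gives a responder and the general statements on rescue give a failure.

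The size rests on assumed rates of late visits and rescue, since the documents give none. On those assumptions no more than one or two subjects are likely to be affected, in either direction. The boundary p-values show only that a single classification can matter in a close result. They do not show that the trial's conclusion is at risk. Sample size and stated power are untouched.

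**What to change.** 1. In the Table 3 footnote, change condition (ii) to: *have not started rescue medication before that scheduled POD15 assessment*.
2. Add one sentence to SAP 6.4.2 giving the primary-endpoint status of subjects rescued at Visit 5 after the assessments, and reconcile it with SAP 10.1.3 item 5 and Protocol 9.4.2 and 10.3.2. The footnote change alone is not enough: a subject with zero cells at POD8 and at a late Visit 5, rescued there for pain, would then be a cell responder by observation, while Protocol 9.4.2 calls every rescued subject a failure.

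The cost is one phrase, one sentence and one date comparison in the programming. Subjects who are never rescued are unaffected by either change, and sample size and stated power stay as they are. The re-examination of analysis visits that SAP 6.3.5 already schedules before database lock is the natural occasion.

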6.4 Statistical/Analytical Issues

6.4.1 Adjustments for Covariates

The analysis of the continuous secondary efficacy endpoints will be adjusted for baseline values as a covariate in the analyses of covariance (ANCOVA).

6.4.2 Rescued Subjects

Any subject not responding to the study drug because of lack of efficacy at any time after randomization at Visit 2/POD1 may be rescued and placed on an appropriate alternative therapy determined by the Investigator.

The efficacy assessments performed after starting rescue medication will be excluded from the efficacy analyses.

For the primary efficacy endpoints, subjects who are rescued at any time after the first dose of study drug and before the efficacy assessments at POD15 will be considered as treatment failures (Non-responders). The same approach will be applied to derive the secondary endpoint of sustained ACF grade =0.

For both categorical and continuous secondary efficacy endpoints of ACC grade, ocular pain grade and ACF grade, the last observation carried forward (LOCF) approach will be used to impute the data for each Analysis Visit after starting rescue medication.

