The primary efficacy analyses to compare APP13007 against placebo will be conducted on the Intent-To-Treat (ITT) population using the Pearson Chi-square statistic. Fixed sequence testing will be employed to maintain the 2-sided alpha = 0.05. The primary analyses will first test the difference in the proportion of subjects with ACC count = 0 (Grade = 0) at POD8 (Visit 4) maintained through POD15 (Visit 5) between treatment groups. If the test is statistically significant at the 2-sided alpha = 0.05 level in favor of APP13007, the difference in the proportion of subjects with Ocular Pain Grade = 0 at POD4 (Visit 3) maintained through POD15 (Visit 5) between treatment groups will be tested at the two-sided alpha = 0.05 level.

Analyses of Secondary Efficacy Endpoints:

Mean change-from-baseline in ACC Grade, Ocular Pain Grade, ACF Grade and visual acuity at PODs 4, 8 and 15 will be analyzed using an analysis of covariance (ANCOVA). The ANCOVA model will include treatment as a fixed effect and baseline as a covariate. The rest of secondary efficacy endpoints will be analyzed using the same method described for the primary efficacy endpoints. Rescued subjects will be considered to be treatment failures.

Safety Analysis:

The safety analysis will summarize ocular treatment emergent AEs (TEAEs) in the study eye and ocular AEs for the non-study eye. Ocular and non-ocular TEAEs will be summarized similarly.

The other safety endpoints will be summarized as discussed in the Statistical Considerations section of the protocol.

STUDY DESIGN

Figure 1: Study Schematic

[figure not shown]

Table 1: Schedule of Events

PROCEDURE/ASSESSMENTS ¹	Visit 1 Screening (Day -28 to -1)	Surgery ² Day 0	Visit 2 POD1 ³	Visit 3 POD4 (±1 Day)	Visit 4 POD8 (±1 Day)	Contact POD14	Visit 5 POD15 (+1 Day) ⁴	Visit 6 POD22 (±2 Days) ⁵
ICF, Demography, Medical History	X							
Determine Eligibility, Review Inclusion/Exclusion Criteria	X		X					
Urine pregnancy test only for women of child-bearing potential			X				X	
Ocular Symptoms Assessment ⁶	X		X	X	X		X	X
ETDRS Visual Acuity	X		X	X	X		X	X
Slit Lamp Biomicroscopy ⁷	X		X	X	X		X	X
Indirect Ophthalmoscopy (dilated)	X							X
IOP (Goldmann applanation tonometry) ⁸	X		X	X	X		X	X
Randomization			X					
Dispense Study Drug			X					
Study Drug Dosing BID for 14 days (POD1 to POD14) ⁹			X	X	X	X		
Dispense Diary Card (with instructions for completion)			X	X	X			
Contact Subject ¹⁰						X		
Collect Study Drug							X	

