10. EFFICACY ANALYSES

All efficacy analyses will be performed using the ITT population. In addition, analyses of the primary efficacy endpoints will be performed using the PP population as a sensitivity analysis. All efficacy analyses and summaries will be based on assessments in the study eye for each subject.

The data for subjects who are rescued at any time after the first dose of study drug and before the efficacy assessments at POD15 will be handled as described in [Sections 6.4.2](#) and [6.4.3.1](#). The data for subjects who prematurely discontinue the study without taking any rescue medications will be handled as described in [Section 6.4.3.1](#).

The Analysis Visits (PODs 4, 8 and 15) defined in [Section 6.3.5](#) will be employed in the efficacy analyses.

Baseline values for the efficacy endpoints are defined as the assessment values obtained at POD1 pre-dose.

All efficacy data will be presented in listings.

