10.1.2 Primary Analysis

The Pearson's Chi-square test will be used to test the null hypothesis that there is no difference between treatment groups for the primary efficacy endpoints:

1. The proportion of subjects with ACC count = 0 (ACC grade = 0) at POD8, maintained through POD15
2. The proportion of subjects with Ocular Pain grade = 0 at POD4, maintained through POD15

Since the treatment comparisons of the primary efficacy endpoints are in sequential order, the fixed-sequence hierarchical testing approach will be used to adjust for multiple comparisons. The primary analysis will first compare the proportion of subjects with ACC count = 0 (ACC grade = 0) at POD8, maintained through POD15, between APP13007 and placebo. If the test is statistically significant at the 2-sided $\alpha = 0.05$ level in favor of APP13007, the comparison of the proportion of subjects with Ocular Pain grade = 0 at POD4, maintained through POD15, between APP13007 and placebo will be tested at the two-sided $\alpha = 0.05$ level.

Under the hierarchical testing scheme, once the two-sided p-value exceeds 0.05, the endpoint further down in the sequence will not be claimed for statistical significance.

The tabulated summary of the two endpoints will include the Responder (Response =Yes) and Non-responder (Response=No) for ACC count = 0 (ACC grade = 0) at POD8, maintained through POD15, or for Ocular Pain grade = 0 at POD4, maintained through POD15, and the 95% confidence interval (CI) for Responder. The treatment difference of the Responder rates with the associated 95% CI will be presented. The Response will be further categorized as:

Yes (Responder):

- Yes – Without imputed data
- Yes – With imputed data

No (Non-responder):

- No – With Rescue Medication Use
- No – Without Rescue Medication Use
- No – With imputed data

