10.2.2 Analysis of Secondary Efficacy Endpoints

10.2.2.1 Analysis of Categorical Endpoints of ACC, Ocular Pain and ACF

The secondary efficacy endpoints (categorical endpoints) of ACC grade, Ocular Pain grade and ACF grade will be analyzed and summarized in the same manner as described for the primary efficacy endpoints ([Section 10.1.2](#)). The imputation for missing values for the categorical endpoints is described in [Section 6.4.3.1](#). The proportion of subjects with ACC grade = 0, Ocular Pain grade = 0, and ACF grade = 0 at PODs 4, 8, and 15 will be plotted separately for each of these endpoints.

In addition, the ACC grade, Ocular Pain grade and ACF grade will be tabulated, including the number and percentage of subjects in each grade category, using the observed data only.

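### Post-rescue LOCF in SAP 6.4.2 can make a rescued subject a responder in the by-visit ACC, pain and ACF proportions, at odds with the protocol synopsis; BCVA is missing from both SAP post-rescue LOCF lists

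*SAP*

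**What the plan says.** SAP 6.4.2 drops every efficacy assessment made after rescue starts. It scores rescued subjects as Non-responders for the two primary endpoints and for sustained ACF grade 0. For visits after rescue on the remaining endpoints it prescribes: "For both categorical and continuous secondary efficacy endpoints of ACC grade, ocular pain grade and ACF grade, the last observation carried forward (LOCF) approach". SAP 6.4.3.1 repeats that three-endpoint list for rescued subjects who also leave the study, and defines the value carried: "The last observation will be the last assessment value after the first dose of study drug and prior to starting rescue medication". Its closing rule opens "If no data can be carried forward (i.e., missing assessments at POD 4 visit or no available post-baseline assessments" and makes such a subject a Non-responder on categorical endpoints.

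SAP Section 10 sends rescued subjects to the rules in 6.4.2 and 6.4.3.1; in its wording, data for those "rescued at any time after the first dose of study drug and before the efficacy assessments at POD15 will be handled as described in" these two places. SAP 10.2.2.1 takes over the primary method and display for the by-visit proportions and adds: "The imputation for missing values for the categorical endpoints is described in" Section 6.4.3.1. In the SAP 10.1.2 display, responders are split only by whether data were imputed (one of the two rows is "Yes – With imputed data"). Rescue is named only among the non-responders, in the row "No – With Rescue Medication Use".

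The protocol synopsis, in its paragraph on secondary endpoints, has the endpoints outside the ANCOVA analysed "using the same method described for the primary efficacy endpoints. Rescued subjects will be considered to be treatment failures". Protocol 10.3.2 is narrower. It applies failure to the primary endpoints and to those secondary endpoints that are *relevant*, a term it does not define, and it assigns post-rescue LOCF to continuous secondary endpoints. Protocol 10.1 leaves analysis details to the SAP.

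**The concern.** Rescue can be triggered by one parameter while another stands at 0. Under protocol 9.4.1 a rise in cell count alone is a ground for rescue, and so is pain or photophobia that persists although cells or flare have improved. Carrying the last pre-rescue grade forward then counts as a success, at later visits, a subject whose study drug was stopped for lack of efficacy. The synopsis says the opposite.

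At stake are the by-visit proportions, which SAP 10.2.2.1 also plots. The display would not tell a reader how many responders had been rescued.

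BCVA raises a smaller, separate question. Its post-rescue values are excluded along with all other efficacy assessments, but the SAP's post-rescue rule does not name it. One programmer could leave those values missing and another could carry them forward, giving different ANCOVA results.

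**Working it through.** **Rules side by side, for a rescued subject**

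| Endpoint | Protocol synopsis | Protocol 10.3.2 | SAP 6.4.2 / 6.4.3.1 |
|---|---|---|---|
| Two primary endpoints | failure | failure | Non-responder |
| Sustained ACF = 0 | failure | failure if *relevant* | Non-responder |
| By-visit ACC, pain, ACF = 0 | failure | failure if *relevant* | LOCF |
| Change in ACC, pain, ACF grade | not applicable to a mean | LOCF | LOCF |
| Change in BCVA | not applicable to a mean | LOCF | not named |

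The third row conflicts with the synopsis and extends the LOCF of protocol 10.3.2. The last row is the BCVA gap.

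**Trace 1, carried-forward value.** Pain is rated before the eye is examined (protocol 7.2.2.2). A subject has pain 0 at the POD8 visit and is rescued that day for cells. Later values are excluded, so pain 0 is carried to POD15. By visit the subject is a POD15 pain responder, in the imputed Yes row. On the primary pain endpoint the same subject is a failure.

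**Trace 2, observed value.** SAP 6.3.5 assigns unscheduled assessments to windows, and the POD15 window opens on Study Day 12. A subject seen unscheduled on Day 13 has pain 0 and is then rescued. The scheduled POD15 value is excluded, so the Day 13 value is the one left in the window. Nothing needs imputing, and the subject can sit in the Yes row without imputed data. The same can happen at POD8 from Study Day 7.

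**Which visits.** POD15 is affected by any rescue before the POD15 assessments. A rescue at that visit does not matter, because protocol 9.4.2 puts the assessments first. POD8 is affected only by rescues before the POD8 assessments. POD4 is hardly affected: with no earlier post-dose value the subject is a Non-responder, which leaves only an unscheduled grade 0 inside the POD4 window.

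**Size.** The plan has no figure for this effect. Its only input here is 185 per arm, which reproduces: 175 / 0.95 = 184.2, rounded up to 185. Rescue rates and pre-rescue grades are not given, so the rest is assumed, for pain:

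- rescue before POD15 (placebo / APP13007): 10%/3%, 20%/5% or 30%/10%
- share *f* of rescued subjects whose last post-dose, pre-rescue pain was 0: 20% to 40%, equal in both arms (those with nothing to carry count as not 0)
- 25% to 75% of these rescues fall before the POD8 assessments, with the same timing in both arms and the same *f* for early and late rescues

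Relative to Non-responder scoring, gain per arm = rescue rate × *f*; subjects = gain × 185; shrinkage of the difference = placebo gain − APP13007 gain; POD8 shrinkage = POD15 shrinkage × fraction rescued before POD8.

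| Rescue rates | Placebo gain, points (subjects) | APP13007 gain, points (subjects) | POD15 shrinkage | POD8 shrinkage |
|---|---|---|---|---|
| 10%/3% | 2.0–4.0 (4–7) | 0.6–1.2 (1–2) | 1.4–2.8 | 0.35–2.10 |
| 20%/5% | 4.0–8.0 (7–15) | 1.0–2.0 (2–4) | 3.0–6.0 | 0.75–4.50 |
| 30%/10% | 6.0–12.0 (11–22) | 2.0–4.0 (4–7) | 4.0–8.0 | 1.00–6.00 |

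Example: 10% × 20% − 3% × 20% = 2.0 − 0.6 = 1.4 points at POD15, and 1.4 × 0.25 = 0.35 at POD8. With equal rates and equal *f* the shift is 0. The direction reverses only if *f* on APP13007 exceeds *f* on placebo by more than the rescue-rate ratio: 10/3 = 3.3, 20/5 = 4.0, 30/10 = 3.0. For ACC and ACF the effect should be smaller, because a grade of 0 is unlikely on the parameter that triggered rescue.

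**The case against.** The strongest reply is that the SAP rule is a choice, not a slip. SAP 6.4.2 names categorical endpoints expressly and gives failure scoring by name to sustained ACF. The Amendment 1 summary of changes says the LOCF wording for secondary endpoints was clarified in response to FDA comments. On this view the SAP supplies what protocol 10.3.2 left open with *relevant*, and the residue is one synopsis sentence. This largely stands as a reason to keep LOCF as the main version. It does not reconcile the synopsis, and the documents do not show what the comments asked for.

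On BCVA, protocol 10.3.2 already supplies LOCF. SAP 10.2.2.2 also sends BCVA to 6.4.3.1, whose intermittent-missing rule covers efficacy endpoints in general. The first part stands: the intended rule can be found. The second is a stretch, since the SAP does not say that values excluded after rescue count as intermittently missing.

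On the display, cumulative rescue counts (SAP 10.2.2.3), observed-data grade tables and listings give partial context. None of the tables crosses rescue with response, but an extra row is a matter of preference.

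A reader might infer that the SAP contradicts itself, because 10.2.2.1 borrows a primary display with a rescue row under No. The documents do not support that: Section 10 and 10.2.2.1 both point to the rescue and imputation sections, so response is settled there before the subject is placed in a row.

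**Conclusion.** The point holds and is minor. Followed as written, the SAP scores some rescued subjects as by-visit responders, which conflicts with the synopsis and goes further than protocol 10.3.2. They may sit in either Yes row, and neither row shows rescue. BCVA is absent from two SAP lists where the protocol makes no exception.

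Only secondary endpoints outside the fixed sequence are touched: the by-visit proportions and the BCVA ANCOVA. The size cannot be estimated from the documents. The 1.4 to 8.0 points for pain at POD15 rest wholly on the assumed rescue rates and shares, and the upper end needs 30% placebo rescue with 40% of those subjects pain-free beforehand.

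A reader might infer that the rule favours APP13007 or puts an efficacy claim at risk. The documents do not support that. No confirmatory test uses the rule, and if rescue is commoner on placebo with similar pre-rescue shares at grade 0, the rule narrows the difference.

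**What to change.** Before database lock:

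1. Keep LOCF as the main version. Add a supportive by-visit analysis of ACC, pain and ACF that scores as Non-responder every subject who started rescue before the scheduled assessment for that Analysis Visit. This must include subjects with an unscheduled pre-rescue value of 0 in the same SAP 6.3.5 window.
2. Reconcile the synopsis sentence and protocol 10.3.2 with SAP 6.4.2 by naming which secondary endpoints use failure scoring and which use LOCF.
3. Add BCVA to the post-rescue LOCF lists in both SAP 6.4.2 and 6.4.3.1 to match protocol 10.3.2, or record why it is left out if the FDA comments require that.
4. Optionally, flag rescued subjects under both Yes rows of the display.

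The cost is one extra derivation, one extra table and wording in two SAP sections, plus the reconciliation of the protocol text.
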